## 8.1 General Measures

### 8.1.1 Inclusion/Exclusion

This form lists each inclusion and exclusion criterion to document eligibility. Eligibility is assessed continually as appropriate. Only participants who continue to meet study eligibility criteria are allowed to continue with the screening process, consent and randomization.

### 8.1.2 Locator Form

A locator form is used to obtain information to assist in finding participants during treatment and at follow-up. This form collects the participant's current address, email address, and phone numbers. In order to facilitate locating participants if direct contact efforts are unsuccessful, addresses and phone numbers of family/friends who may know how to reach the participant are collected, as well as additional participant information such as social security number and other information to aid in searches of public records. This information will be collected at screening and will be updated at each visit. No information from this form is used in data analyses.

### 8.1.3 Demographics Form

The Demographics form collects information about demographic characteristics of the participant, including date of birth, ethnicity, race, education, employment status, and marital status. This form is completed at screening.

### 8.1.4 Study Completion Form

This form tracks the participant's status in the study. It is completed at the final postnatal visit or once the 6-month follow-up visit window lapses for participants who do not complete this final follow-up. This form is used in data analyses to address variables such as treatment retention and completion. This form also provides a location for the site PI attestation of review of all study data.

## **8.2 Clinical and Safety Assessments**

### **8.2.1 Adverse Events (AEs) and Serious Adverse Events (SAEs)**

At each visit the study navigator assesses for AEs and SAEs by asking the study participant, "How have you been feeling since your last visit?" AEs and SAEs may also be spontaneously reported to study staff at any visit following consent. AEs and SAEs suggesting medical or psychiatric deterioration will be brought to the attention of a study clinician for further evaluation and management. Visits will emphasize overdose risk and risk-management. Any reported overdose is recorded as an AE or SAE, or in a separate form. AE and SAE reporting is according to the reporting definitions and procedures outlined in the protocol and in accordance with applicable regulatory requirements.

For the purpose of this study, the following AEs do not require reporting in the data system but is captured in the source documentation as medically indicated:

Grade 1 (mild) unrelated adverse events. This would typically include mild physical events such as headache, cold, etc., that were considered not reasonably associated with the study intervention.

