#### 7.5 Treatment/Intervention

**Standard care.** The standard care condition at Magee and the University of Utah hospitals includes brief case management and referral. The brief case management involves the participant speaking to a hospital social worker who conducts a patient needs assessment in the areas of behavioral health and social services. All patients will be referred to MAT and any identified behavioral health or social service needs. For MAT, Magee-Womens Hospital offers resources for onsite induction to methadone or buprenorphine (mono-product), with continued methadone maintenance only provided by community partners and continued buprenorphine offered by an internal Magee clinic or community partners. University of Utah patients are offered buprenorphine induction and maintenance (buprenorphine-naloxone product) at a local University of Utah outpatient clinic or from community partners. Methadone services for University of Utah patients are only provided by community partners. Staff social workers at Magee and the University of Utah will be provided with information on the study each quarter during the study recruitment phase and be instructed to closely follow and not deviate from their hospital standard care protocol. These quarterly meetings/trainings will be delivered in order to prevent threats to internal validity and biasing study outcomes.

**Patient navigation (PN).** Details of the navigation can be found in the PN Intervention Manual. The PN intervention will be delivered by the study navigator. Table 4 contains details of the PN intervention. The PN intervention will initiate following participant recruitment. *It is important to note that in Table 2, PN sessions do not strictly coincide with specific weeks of pregnancy since the women can be recruited up to ≤32 weeks of gestation.* The prenatal portion of the intervention includes up to 10 sessions delivered prior to delivery. The postnatal portion of the intervention will be delivered as 4 sessions over 8 weeks. Women who complete the intervention before delivery will receive regular calls/texts until delivery wherein the navigator will encourage and reinforce abstinence and treatment retention (see SOP for continued engagement). All contact will be reported by staff in a participant contact log developed for the study that will be used to quantify level of patient contact.

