## **12.0 DATA AND SAFETY MONITORING PLAN**

### **1.0 OVERSIGHT OF CLINICAL RESPONSIBILITIES**

#### **A. Site Principal Investigator**

Each participating site's Principal Investigator (PI) is responsible for study oversight, including ensuring human research subject protection by designating appropriately qualified, trained research staff and medical clinicians to assess, report, and monitor adverse events. All adverse events (AEs) occurring during the course of the clinical trial will be collected, documented, and reported by the investigator or sub-investigators according to the Protocol, see Appendix. The occurrence of AEs and serious adverse events (SAEs) will be assessed at each clinic visit during the study. Serious adverse events will be followed until resolved or considered stable. Reportable AEs are required to be entered into the data system within 7 days of the site staff becoming aware of the event. Reportable SAEs (including death and life-threatening events) are required to be entered into data system within 24 hours of site's knowledge of the event).

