## **Participant Protection**

AEs and concomitant medications will be assessed and documented at clinic visits. Individuals who experience an AE that compromises safe participation in the study will be discontinued from further intervention and provided referrals for other treatment or to specialized care. Study personnel will request that the participant complete an end visit to assure safety and to document outcomes.

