## 14.0 APPENDIX A: ADVERSE EVENT REPORTING AND PROCEDURES

Each participating site's Principal Investigator is responsible for study oversight, including ensuring human research subject protection by designating appropriately qualified and trained study personnel to assess, report, and monitor adverse events. See AE form in the electronic data capture program.

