## **Site's Role in Eliciting and Reporting Adverse Events**

Appropriately qualified and trained personnel will elicit participant reporting of AEs and SAEs at each study visit designated to collect AEs. Adverse events (medical and/or psychiatric) assessment will initiate with participant consent and follow-up will continue through the final assessment. Study personnel will obtain as much information as possible about the reported AE/SAE to complete the AE/SAE forms and will consult as warranted.

Standard reporting, within 7 days of the site becoming aware of the event, is required for reportable AEs. Expedited reporting (within 24 hours of their occurrence and/or site's knowledge of the event) is required for reportable SAEs (including death and life-threatening events). Local sites are responsible for reporting SAEs to the IRB of record, per the IRB or record's guidelines.

Sites are required to enter reportable AEs and SAEs in data capture program. The AE form is used to capture reportable AEs and SAEs (as defined in the protocol) and will be reviewed by the study PI upon submission. Additional information may need to be gathered to evaluate SAEs and to complete the appropriate CRFs and the summary. This process may include obtaining hospital discharge reports, medical records, autopsy records or any other type records or information necessary to provide a complete and clear picture of the serious event and events preceding and following the event. If the SAE is not resolved or stable at the time of the initial report or if new information becomes available after the initial report, follow-up information must be submitted as soon as possible.

Reportable adverse events will be followed until resolution, stabilization or study end. Any serious adverse reactions will be followed until resolution or stabilization even beyond the end of the study.

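### Section 8.2.1 gives adverse-event questioning to the navigator while other sections give it to unnamed trained staff, so who asks standard-care women, and at which visits, is not settled

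*Combined protocol and SAP*

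**What the plan says.** Section 8.2.1 names one person to ask about AEs and serious AEs (SAEs): "At each visit the study navigator assesses for AEs and SAEs by asking the study participant". The question it words is "How have you been feeling since your last visit".

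On the navigator's role, Section 7.5 states "The PN intervention will be delivered by the study navigator". The calls, texts and outreach described there are also part of PN, while standard-care women are described as speaking with a hospital social worker. One other navigator duty carries no arm restriction. Section 8.2.2 has the navigator act on a positive depression or suicidality screen from the Patient Health Questionnaire, which the Section 8.0 schedule gives to both arms.

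Follow-up assessments in both arms are run by a blinded research assistant (Section 7.9.2). Section 7.8 describes a locator check and then a survey, with no AE question, and the Section 8.0 table has no AE row.

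Other sections set a general duty without reference to arm:
- Section 12.0, part A: "The occurrence of AEs and serious adverse events (SAEs) will be assessed at each clinic visit during the study".
- Section 12.0, Participant Protection: "AEs and concomitant medications will be assessed and documented at clinic visits".
- Appendix A, opening paragraph: each site's principal investigator is to protect participants by "designating appropriately qualified and trained study personnel to assess, report, and monitor adverse events".
- Appendix A, on eliciting events: "Appropriately qualified and trained personnel will elicit participant reporting of AEs and SAEs at each study visit designated to collect AEs"; and AE "assessment will initiate with participant consent and follow-up will continue through the final assessment".

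None of these names a role, and the designated visits are not listed.

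**The concern.** The only section that both words the AE question and names an asker chooses the person who delivers the experimental intervention. Read naturally, that ties active safety questioning to contacts that one arm has and the other lacks. An arm asked more often, over shorter recall periods, can show more events with no difference in harm. Equally, events in the less-questioned arm can go unseen.

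The AE data have a use. Section 12.0, part C has the investigators use them to judge whether the benefit-to-risk balance has changed and whether the study should continue, change or stop. The same part has the DSMB review accumulating safety data and advise on halting. The events listed in Appendix A include child protective services involvement, which urine toxicology and the substance-use calendar would not capture.

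There is also a plain operational gap. The sections supplied do not say which person asks a standard-care woman about AEs, and the only person named to act on her positive questionnaire screen is the navigator.

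**Working it through.** The plan states no number of AE enquiries per arm, so there is no figure to reproduce. The inputs come from Section 3.2: up to 10 prenatal PN sessions over 8 to 14 weeks, 4 postnatal sessions over 8 weeks, and 4 assessments in both arms. Baseline precedes randomisation (Section 7.4), which leaves 4 − 1 = 3 shared post-baseline assessments.

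**Enquiries after baseline, with every session held**

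| What counts as an AE visit | PN | Standard care |
|---|---|---|
| A. Sessions and shared assessments | 10 + 4 + 3 = 17 | 3 |
| B. Navigator sessions only | 10 + 4 = 14 | 0 |
| C. Shared assessments only | 3 | 3 |

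With baseline included, A becomes 18 against 4 and C becomes 4 against 4. Calls and texts before delivery are not counted.

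**Timing under A.** Up to the prenatal assessment, 10 + 1 = 11 against 1. From then to about 2 months after delivery, 4 + 1 = 5 against 1. From then to 6 months, 1 against 1. The whole excess of 14 falls before about 2 months after delivery.

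**Attendance.** The documents give none, so take a share *a* of sessions held as an assumption. Under A the PN count is 3 + 14*a*, which is 6.5, 10, 13.5 and 17 for *a* = 0.25, 0.5, 0.75 and 1, against 3. Under C it is 3 against 3 at any attendance.

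**Period covered by the question.** If sessions count as visits, the mean prenatal interval in PN is 8/10 = 0.8 to 14/10 = 1.4 weeks. At half attendance it is 8/5 = 1.6 to 14/5 = 2.8 weeks. In standard care it is about 8 to 14 weeks, assuming the prenatal assessment falls at the end of the prenatal portion in both arms. Under C the period is the same in both arms.

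**Which reading the text supports.** For A or B: Section 8.2.1 names the navigator, whose described contacts are PN sessions. For C: the plan mostly calls PN contacts sessions and assessments visits (Sections 7.3, 7.8 and 8.1.4). Section 8.2.2 says the suicide item is assessed at each visit, and its questionnaire is scheduled only at the four shared assessments. The usage is not strict, since Section 7.8 once calls follow-up appointments sessions.

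**Each reading leaves something to repair.** Under A, no role is named to ask at the shared assessments. Under B, standard-care women get no active questioning, contrary to the arm-neutral duty in Appendix A. Under C, the navigator as asker does not fit Sections 7.8 and 7.9.2, where a blinded research assistant conducts the assessments and no AE step appears.

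**The case against.** The strongest reply is that the plan already covers everyone. Section 12.0 and Appendix A assign AE elicitation for all participants to designated trained staff, from consent to the final assessment. Section 8.2.2 uses the navigator without restriction by arm, which may mean that navigator safety duties span both arms. Role-level detail may sit in documents not supplied: the data-collection SOP, the SOP covering assessment and blinding, the Operations Manual or the AE form. On this view the text needs only tidying.

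Much of this stands. A reader might infer that standard-care women are never asked about AEs. The documents do not support that: the general duty applies to them, and no section says the navigator does not see them. A reader might also take 17 against 3 as the plan's schedule. It is a maximum on one reading, and 3 against 3 is also open.

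The consequence is limited too. Section 10.3 plans no between-arm AE test, and nothing says the DSMB listings are split by arm. Mild unrelated events, which frequent open questioning would most plausibly inflate, need not enter the data system (Section 8.2.1). Urine toxicology and the Timeline Follow Back at every assessment, together with monitoring by site treatment providers (Section 11.13.1), do not depend on the navigator.

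What the reply does not remove is the conflict itself. The general duty names no role and no visits, and the one specific instruction points to the navigator. An SOP that named an asker for standard care would still leave ascertainment unequal if PN sessions also collect AEs.

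**Conclusion.** The concern holds as a failure to reconcile Section 8.2.1 (and 8.2.2) with Sections 7.8, 7.9.2 and 8.0, Section 12.0 and Appendix A. The documents do not settle whether PN sessions are AE-collecting visits. Depending on the answer, post-baseline questioning is up to 17 against 3, up to 14 against 0, or 3 against 3. The two unequal figures assume full session attendance, and 17 against 3 also assumes that somebody asks at every shared assessment.

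On the unequal readings, any arm-level look at AEs in the benefit-to-risk or DSMB review would mix harm with ascertainment. How far AE counts would shift cannot be derived from the documents. The point does not touch the efficacy analyses. It should be corrected because the repair is cheap and the data feed safety decisions.

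**What to change.** 1. In Section 8.2.1 and the Section 8.0 schedule, ask the same AE question in both arms at the three shared post-baseline assessments, after the outcome measures. Word it as *since your last study assessment*, so that it covers the same period in each arm. Record how each event was elicited. Base any arm-level AE summary on events from the shared assessments. List navigator-elicited and spontaneous events separately, and still report all of them for safety.
2. Reconcile Sections 8.2.1 and 8.2.2, Section 12.0 (part A and Participant Protection) and Appendix A on who asks standard-care women and who acts on their positive screens, and list the AE-collecting visits. No clinical rule is proposed here.

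The cost is protocol wording, one schedule row, one form field and one extra listing, with no additional staff or visits. There are two downsides. The arm-level summary rests on longer recall and will miss some events, although the full safety listing keeps those reported by other routes. There is also a small risk that an answer reveals the arm to the assessor; asking after the outcome measures limits this at that assessment.

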### **7.9.2 Maintenance of the Blind**

The individuals blinded to the study condition will be those conducting the study assessments. The baseline assessment will be blinded given that the randomization will not be revealed until after the assessment is completed. The follow up assessments will be conducted by a blinded research assistant.

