### **7.9.3 Breaking the Blind**

As the research assistant is the only blinded party, there is no scenario in which the blind will need to be broken. Investigators providing clinical management and decision-making are informed of each participants randomization result.

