## **7.10 Participant Reimbursement**

Women will receive \$30 for enrolling in the study and completing the baseline assessment, \$40 for completion of the second assessment, \$50 for the third assessment, and \$75 for the final assessment. Patients that complete all 4 assessments will be given a completion bonus of \$50. Patients will also be provided with a \$10 compensation for each navigator session they attend to cover costs associated with transportation and/or parking. Participant compensation administration will be carried out by the study project coordinator or research assistants.

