## 8.0 STUDY ASSESSMENTS

*A full and complete list of all assessments used in the study is to be included in the following sections.*

Outcome	Domain	Name	Source	Screen	Base	PreNat	2mo	6mo
1/2ary	Engage	Treatment Services Review	Self-Report		x	x	x	x
1/2ary	SUD	Timeline Follow Back	Self-Report		x	x	x	x
1ary	Engage	Substance use treatment visits	Medical record		x	x	x	x
1ary	Engage	Psychiatric care visits	Medical record		x	x	x	x
1ary	SUD	Urine toxicology	NA	x	x	x	x	x
1ary	Engage	Social service visits	Agency record		x	x	x	x
2ary	HIV/HCV risk	Risk Behavior Assessment	Self-Report		x	x	x	x
2ary	Social	Maternal Social Support Index	Self-Report		x	x	x	x
2ary	Social	Parenting Stress Index-Short Form	Self-Report		x	x	x	x
2ary	Social	Maternal Attachment Inventory	Self-Report		x	x	x	x
2ary	Engage	Adequacy of Prenatal Care Utilization	Medical record				x	
2ary	Engage	Pre/post maternal care visits	Medical record		x	x	x	x
2ary	Engage	Pediatric visits	Medical record		x	x	x	x
2ary	SUD	Neonatal abstinence syndrome	Medical record				x	
2ary	Engage	Pre/post maternal care visits	Medical record		x	x	x	x
2ary	Engage	Pediatric visits	Medical record				x	x
Covar	SUD	Drug Abuse Severity Test 10	Self-Report		x	x	x	x
Covar	SUD	Alcohol Use Disorder	Self-Report		x	x	x	x

		Identification Test						
Covar	SUD	Fagerstrom Test for Nicotine Dependence	Self-Report		x	x	x	x
Covar	Health	Short Form 36	Self-Report		x	x	x	x
Covar	Psych	Patient Health Questionnaire	Self-Report		x	x	x	x
Covar	Social	Addiction Severity Index (employment)	Self-Report		x	x	x	x
Covar	SUD	DSM 5 Checklist	Self-Report	x	x	x	x	x

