### **8.2.2 Suicidal Behavior Evaluation**

Within the Patient Health Questionnaire is embedded a validated single item suicide screening tool. This item is assessed at each visit. If the participant screens positive for depression, the navigator will ensure the participant contacts the Resolve Crisis Center to arrange for follow up ([name]) within the University of Pittsburgh or the Crisis and Interventional and Hospital Diversion Crisis Line within the University of Utah ([name]). If the participant screens positive for suicidality, the navigator will immediately follow the study Suicide Management Plan (see REDCap form). Similarly, if the participant appears to be intoxicated or reports experiencing symptoms of opioid withdrawal, the navigator will immediately notify the site study physician who can further assess and direct steps for possible additional care depending on participant need.

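### Section 8.2.1 gives the adverse-event question to the unblinded navigator who delivers PN and does not settle who asks standard-care women, so recorded non-fatal overdose may not be comparable between arms

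*Combined protocol and SAP*

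**What the plan says.** **Who asks.** Section 8.2.1 of the combined protocol and SAP: "At each visit the study navigator assesses for AEs and SAEs by asking the study participant". The scripted wording is a general enquiry about how she has felt since her last visit. It does not name overdose, although the same section says visits will emphasise overdose risk and that any reported overdose is recorded as an AE, as an SAE or on a separate form. Spontaneous reports to study staff are also accepted.

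**Who the navigator is.** Section 7.5: "The PN intervention will be delivered by the study navigator". Standard care is a hospital social worker's needs assessment and referral, with no AE task stated.

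**Who is blinded.** Section 7.9.2: "The follow up assessments will be conducted by a blinded research assistant". Section 7.9.3 begins: "As the research assistant is the only blinded party". So the navigator is unblinded. No section gives the research assistant the AE question.

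**Arm-neutral text.** Section 12.0, part A: "The occurrence of AEs and serious adverse events (SAEs) will be assessed at each clinic visit during the study". That part has the site PI designate trained research staff and clinicians for AE work. The Participant Protection paragraph of section 12.0 also places AE assessment at clinic visits. Appendix A has trained personnel ask at study visits designated for AE collection, from consent to the final assessment. None of these names the person or lists the visits.

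**Reporting.** Section 10.3 does not list AEs or overdose among its comparisons. Section 12.0, part C, and Appendix A promise the DSMB AE listings and SAE summaries, with no split by arm stated.

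**The concern.** A comparison of harms between arms needs the same question, put by the same kind of person, at the same times. Section 8.2.1 as written does not secure this. Either the PN arm is questioned more often, or the person who delivers the intervention does the questioning at the assessments, which does not fit section 7.9.2.

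Overdose is one of the harms that section 1.1 hopes treatment linkage will reduce, and section 12.0, part C, uses AE data to judge benefit against risk. Section 2.1 presents the study as the foundation for a fully powered trial. A non-fatal overdose count that cannot be compared between arms would be a poor thing to carry forward. Extra questioning in PN adds recorded PN events, so it could make PN look worse or mask a benefit. It would not hide harm from PN. If the navigator asks at equal frequency in both arms, the direction of any effect is unknown.

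**Working it through.** The plan states no figure on this point, so there is none to reproduce first.

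**1. What counts as a visit.** Two readings are possible.

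- *PN sessions count.* This fits the choice of the navigator as questioner.
- *Only assessments count.* Section 8.2.2 says of the suicide item in the Patient Health Questionnaire: "This item is assessed at each visit". The section 8.0 table schedules the "Patient Health Questionnaire" only at the four assessments. Section 7.10 pays "for each navigator session they attend", so it calls PN contacts sessions. Section 12.0 speaks of clinic visits, and Appendix A of designated visits. This reading has the better textual support.

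**2. Scheduled contacts after randomisation.** Inputs: up to 10 prenatal and 4 postnatal sessions (section 7.5); 4 assessments in both arms (section 3.2), of which baseline precedes randomisation (section 7.4).

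- Sessions count: 10 + 4 + 3 = 17 in PN, 3 in standard care.
- Only assessments count: 3 in each arm.

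**3. Attendance model, if sessions count.** Assumptions, none of them from the documents:

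- equal true risk, with events uniform from randomisation to 26 weeks after delivery;
- delivery 1 week after the prenatal portion ends, and the 2-month assessment 8.7 weeks after delivery;
- prenatal sessions evenly spaced, postnatal sessions every 2 weeks;
- the same attendance probability a at every contact in both arms, and full recall.

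The prenatal portion is 8 or 14 weeks, the limits in section 3.2. An event followed by m scheduled contacts is captured with probability 1 − (1 − a)^m.

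Standard care, 14-week portion, a = 0.5: total time is 14 + 1 + 26 = 41 weeks. The three windows last 14, 9.7 and 17.3 weeks and are followed by 3, 2 and 1 assessments. Capture = (14 × 0.875 + 9.7 × 0.75 + 17.3 × 0.5)/41 = 0.687. Adding the 14 sessions gives 0.773 in PN.

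| a | 14 weeks: standard care, PN, ratio | 8 weeks: standard care, PN, ratio |
|---|---|---|
| 0.5 | 0.687, 0.773, 1.12 | 0.655, 0.734, 1.12 |
| 0.7 | 0.843, 0.870, 1.03 | 0.821, 0.848, 1.03 |
| 0.9 | 0.955, 0.958, 1.00 | 0.948, 0.950, 1.00 |

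With 6 true events per arm (assumed), the largest excess is 6 × (0.773 − 0.687), about 0.5 recorded event. The ratio stays modest because all 14 extra contacts are over by 8 weeks after delivery. Later events have the same remaining assessments in both arms.

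**4. Recall loss (assumed).** Let the chance of reporting at a contact be a × 0.5^(weeks since event/h). Over a from 0.9 to 0.5 and both portion lengths, the ratio is 1.02 to 1.22 for h = 52 weeks and 1.05 to 1.32 for h = 26 weeks.

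**5. Only assessments count.** The schedule is the same in both arms, so the ratio is 1.00 at equal attendance. The effect of an unblinded questioner cannot be computed from the documents.

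**6. With the same question at the three assessments.** The ratio is 1.00 at equal attendance. At 80% in PN against 70% in standard care (assumed) it is 0.903/0.843 = 1.07 (14 weeks) or 0.888/0.821 = 1.08 (8 weeks).

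**7. Precision of a by-arm table with 61 women per arm.** For 0/61 the exact two-sided 95% upper limit is 5.9%. For an illustrative 3/61 against 6/61 the difference is −4.9 points (Newcombe 95% CI −15.4 to +5.1).

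**The case against.** The strongest reply is that the plan already covers both arms. Section 8.2.1 speaks of the study participant without limiting this to PN. Section 12.0 and Appendix A have AEs assessed in all participants, from consent to the final assessment, and section 11.13.1 makes site treatment providers responsible for noticing deterioration. Naming the questioner is the sort of detail that belongs in SOPs and in the AE form, which the protocol cites but which are not in the public file. The better-supported reading of a visit gives 3 against 3. Even on the other reading, the modelled excess is about half an event in six, far smaller than the sampling error. Overdose is neither a listed outcome (sections 4.1 and 4.2) nor part of H1 to H3, and section 10.2.2 disclaims definitive testing.

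Most of this stands, and it sets the grade. A reader might infer that standard-care women are not asked at all, or that questioning runs 14 against 0. The documents do not support that, because the arm-neutral text shows an intent to ask everyone. A reader might also infer that harm from PN could go unseen. Extra questioning in PN works the other way, and Appendix A requires deaths to be reported however they come to light.

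What remains is that section 8.2.1 states a rule: the interventionist asks. The arm-neutral text does not replace that rule with a common questioner, question or schedule. The lack of a stated by-arm table does not show that none will be made; alone it would be only a missing detail.

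**Conclusion.** The concern holds in a limited form. Section 8.2.1 assigns the AE question to the unblinded navigator who delivers PN, other sections assign it to unspecified staff, and the plan does not reconcile them or ask about overdose in the scripted question. Capture of AEs and non-fatal overdose may therefore differ by arm.

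The size that can be modelled is small: a ratio of 1.00 to 1.12 on attendance alone if PN sessions count as visits, up to 1.32 only with an assumed 26-week recall half-life, and 1.00 if only assessments count. These figures rest on the timing, attendance and recall assumptions listed above. Any effect of an unblinded questioner is unknown. No planned hypothesis is affected. If the unseen SOPs or AE form already set one common question, only the request for a by-arm table is left. Grade: consider.

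**What to change.** **Section 8.2.1.** At the prenatal, 2-month and 6-month assessments, the blinded research assistant asks every woman in both arms the same AE question and the same overdose question. Each covers the time since her last completed assessment, and positive answers go to the study clinician. Navigators still report any AE they learn of. The AE form records the source. Add a matching overdose row to the section 8.0 table.

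**Section 10.3 and the DSMB report.** For all randomised women, by assigned arm, give the number and percentage with overdose and with maternal death, from randomisation to 6 months after delivery or earlier exit. Give the risk difference with a 95% Newcombe interval and no test. Show all events, separating those found at the common assessments from those known only through navigator contact or other reports. Count deaths from any source. Show assessment completion by arm, since unequal completion leaves some imbalance.

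**Cost.** Two paragraphs, one table row and an IRB-approved amendment; no new visit. Asking takes 122 × 3 = 366 questionings × 2 minutes (assumed)/60 = about 12 hours. An answer may reveal the arm, but the added risk is small because the Treatment Services Review is already collected at those assessments. The intervals will be wide, so the table is a descriptive signal only.

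**Optional.** Separate chart abstraction for overdose would take 366 × 5 to 10 minutes (assumed), about 31 to 61 hours. Record capture may itself favour PN through better linkage: 50% against 40% (assumed) gives a ratio of 1.25 on records alone.
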